16.1.5. Sensitivity Analysis of Primary Efficacy Variable(s)

The sensitivity analyses will be conducted similar to the primary efficacy analysis including the repeated measure GLM using the PP population.

16.2. Secondary Efficacy

Secondary efficacy variables will be analyzed using both the mITT as well as the PP population.

16.2.1. Secondary Efficacy Variables & Derivations

- Change in mean sitting SBP

Change in mean sitting SBP between Visit 2 (Week 0) and Visit 4 (Week 8).

- Change in mean sitting DBP and SBP

Document: \\weedc-vnasc01\Biosdata\Menarini\NebAml\ZZA67778\Biostatistics\Documentation\SAP\SAP_Menarini_MEIN21AmNe-Hyp001_Final_V1.0

Author: [name]

Version Number:

Final V1.0

Version Date:

11Nov2022

Template No.: CS_TP_BS016 Revision 7

Reference: CS_WI_BS005

Effective Date: 01Nov2021

Change in mean sitting DBP and SBP between Visit 3 (Week 4) and Visit 4 (Week 8) in patients under extemporaneous combination of NEB/AML 5/5 mg versus patients uptitrated to the extemporaneous combination of NEB/AML 5/10 mg.

- Number and proportion of patients achieving the BP goal

Number and proportion of patients achieving the BP goal (sitting SBP/DBP < 130/80 mmHg) at Visit 2 (Week 0), Visit 3 (Week 4) and Visit 4 (Week 8).

16.2.2. Analysis of Secondary Efficacy Variables

16.2.2.1. Change in mean sitting SBP between Visit 2 (Week 0) and Visit 4 (Week 8)

Change from baseline in sitting SBP from prior and post combination therapy will be compared using paired t-test. The p-value will be presented using a paired t-test comparing mean at baseline and mean at Week 8. The secondary endpoint will be presented in a descriptive manner using n, mean, median, SD, Q1, Q3, and minimum and maximum. Assumption of normality will be investigated using Wilk-Shapiro test. If violation is observed, then paired t-test will be replaced by Wilcoxon signed rank test.

Additionally, the secondary end point of change in SBP between Visit 2 and Visit 4 will be analyzed using a repeated measures GLM as described in Section 16.1.4 with Age (Years), Gender, body mass index, and baseline SBP as covariates to identify the effect of covariates and interaction between the covariates.

16.2.2.2. Change in mean sitting DBP and SBP between Visit 3 (Week 4) and Visit 4 (Week 8)

Change in sitting SBP and DBP between patients under extemporaneous combination of NEB/AML 5/5 mg versus patients uptitrated to the extemporaneous combination of NEB/AML 5/10 mg will be compared using independent samples t-test. The secondary endpoint will be presented in a descriptive manner using n, mean, median, SD, Q1, Q3, and minimum and maximum. Assumption of normality will be investigated using Wilk-Shapiro test. If the data is found to be non-Normal, the independent samples t-test will be replaced by Wilcoxon rank-sum test.

Document: \\needc-vnasc01\Biosdata\Menarini\NebAm\ZZA67778\Biostatistics\Documentation\SAP\SAP_Menarini_MEIN21AmNe-Hyp001_Final_V1.0

Author: [name]

Version Number:

Final V1.0

Version Date:

11Nov2022

Template No.: CS_TP_BS016 Revision 7

Reference: CS_WI_BS005

Effective Date: 01Nov2021

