- c. Patients on NEB 5 mg or AML 5 mg will continue the same therapy for 4 weeks (run-in period). Patients on any other BBs will be assigned to monotherapy with NEB 5 mg and the patients on other CCBs (except AML 10 mg) will be assigned to monotherapy with AML 5 mg. The allowed CCBs are: felodipine, lacidipine, lacidipine, nicardipine, nicardipine, nimodipine, and nisoldipine).
- d. Only patients with controlled BP at Visit 3 will receive NEB/AML 5/5 mg for next 4 weeks.
- e. Only patients with uncontrolled BP at Visit 3 will receive NEB/AML 5/10 mg for next 4 weeks.
- f. All concomitant medications ongoing at the time of the consent and any surgery/procedures should be reported.
- g. Pregnancy test (urine): only for females of childbearing potential.
- h. Vital signs will include body temperature, respiratory rate, and pulse rate.
- i. To ensure patient safety, the patients will be contacted over a phone call within 24 hours, in case of any abnormality and clinically relevant laboratory test according to the Investigator's judgment at any visit.

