and AML 5 mg. Patients with controlled BP levels (sitting SBP/DBP <130/80 mmHg) and/or who do not tolerate the treatment or have an adherence range below 80% or above 120%, will be withdrawn from the study.

After 4 weeks  $\pm 2$  days in the assessment period, patients BP will be further evaluated at Visit 3: patients with controlled BP levels (sitting SBP/DBP <130/80 mmHg) will continue the same extemporaneous combination, while patients with uncontrolled BP levels will be uptitrated from extemporaneous combination NEB/AML 5/5 mg to extemporaneous combination of NEB/AML 5/10 mg for further 4 weeks.

At the end of the assessment period (8 weeks  $\pm 4$  days), the patients will attend an End of Treatment Visit 4. To correctly evaluate the additional effect of the combination therapy, the number of patients with uncontrolled BP on NEB or AML monotherapy needs to be balanced at Visit 2. In order to maintain a 1:1 ratio during the assessment period, a cap of 110 patients for each treatment arm (ie. NEB and AML) will be included at Visit 2 in order to maintain a balanced number of uncontrolled patients entering the assessment period for each drug. The evaluation will be done every 50 patients. If the rate of entrance in the assessment period for one of the 2 tested drugs will deviate more than 5%, a corrective measure will be initiated: according to the enrolment site statistics, one or more sites will be informed to enroll a greater number of patients being treated with the least represented drug in the assessment period.

A total number of 290 patients will be screened considering 25% of drop-out rate, to obtain approximately 216 completed patients at the end of the study (Visit 4).

Sitting BP will be measured at all visits before blood sampling. BP will be measured in both arms at the Screening visit (Visit 1) in order to detect possible between-arm differences. The arm with the higher mean DBP will be used in all subsequent visits for BP assessment. Blood pressure measurements should be performed as nearly as possible within the same time frame of the day (7:00 to 12:00 a.m.), on the same arm, possibly by the same member of the site staff/personnel, and using the same calibrated equipment at each visit.

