## 7 STUDY TREATMENT

The following study treatment are administered during:

- Run-in period (Visit 1 to Visit 2): NEB 5 mg tablets or AML 5 mg tablets in patients who were already receiving NEB 5 mg or AML 5 mg or who were on any other BBs or CCBsc, respectively prior to enrolment into the study.
- Assessment period (Visit 2 to Visit 3): Extemporaneous combination of NEB 5 mg and AML 5 mg in patients with uncontrolled BP at Visit 2.
- Assessment period (Visit 3 to Visit 4): Extemporaneous combination of NEB 5 mg and AML 5 mg in patients with controlled BP at Visit 3 and extemporaneous combination of NEB 5 mg and AML 10 mg in patients with uncontrolled BP (sitting SBP/DBP >130/80 mmHg, who tolerated the treatment and whose adherence to the therapies ranges from 80% to 120%) at Visit 2.

Details on the study design is provided in Section 5.

Further details on study treatment is provided below in Table 7.1.

MENARINI	Corp	porate Medical Departm	ent
	Protocol Template		
Identification Number	Version Number	State	Effective date
FORM-000050125	2.0, CURRENT	Effective	08 Jan, 2021

Study Code: MEIN/21/AmNe-Hyp/001

Table 7.1Study Treatment Details	
----------------------------------	--

Study Treatment Name:	Nebivolol Marketing Authorisation Holder : A. Menarini Industrie Farmaceutiche Riunite srl, [name]	Amlodipine Besylate Marketing Authorisation Holder: EG S.p.A. [name] (MAH)
Dosage Formulation:	Tablet	Tablet
Unit Dose Strength(s)/Dosage	5 mg once daily	5 mg/10 mg once daily
Level(s):		
Route of Administration:	Oral	Oral
Dosing Instructions*:	1 tablet of study medication will be administered with a glass of water once daily	1 tablet of study medication will be administered with a glass of water once daily
Packaging and Labelling:	Study medication will be provided in a polyvinyl chloride (PVC)/Aluminum blister	Study medication will be provided in a Aluminum/PVC/polyethylene (PE)/ polyvinylidene chloride (PVDC) blister

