## 12.5.4 Secondary (efficacy) analysis

Secondary efficacy variables will be summarized in a descriptive manner using both the mITT as well as the PP population.

• Change in mean sitting SBP between Visit 2 (Week 0) and Visit 4 (Week 8).

MENARINI	Corporate Medical Department Protocol Template		ient
Identification Number	Version Number	State	Effective date
FORM-000050125	2.0, CURRENT	Effective	08 Jan, 2021

*Study Code:* MEIN/21/AmNe-Hyp/001

- Change in mean sitting DBP and SBP between Visit 3 (Week 4) and Visit 4 (Week 8) in patients under extemporaneous combination of NEB/AML 5/5 mg versus patients uptitrated to the extemporaneous combination of NEB/AML 5/10 mg.
- Number and proportion of patients achieving the BP goal (sitting SBP/DBP <130/80 mmHg) at Visit 2 (Week 0), Visit 3 (Week 4) and Visit 4 (Week 8).

Change in sitting BP between visits will be compared using paired t-test. The p-value obtained from the paired t-test will be presented. Assumption of Normality will be investigated using Wilk-Shapiro test. If the data is found to be non-Normal, the paired t-test will be replaced by Wilcoxon signed rank test.

Similar to the primary end point, the secondary end point of change in SBP between Visit 2 and Visit 4 will be analyzed using a repeated measures GLM. The same covariates as used in the primary analysis will be used for this analysis.

Change in sitting SBP and DBP between patients under extemporaneous combination of NEB/AML 5/5 mg versus patients uptitrated to the extemporaneous combination of NEB/AML 5/10 mg will be compared using independent samples t-test. If the data is found to be non-Normal, the independent samples t-test will be replaced by Wilcoxon rank-sum test.

The secondary endpoints will also be presented in a descriptive manner using n, mean, median, SD, Q1, Q3, minimum, and maximum.

The number of patients achieving the BP goal (sitting BP <130/80 mmHg) will be summarized for Visit 2 (Week 0), Visit 3 (Week 4) and Visit 4 (Week 8) along with percentage and 95% CI. A p-value using McNemar's test will be presented to compare the proportion of patients achieving the BP goal (sitting BP  $\leq$ 130/80 mmHg) between Visit 2 and Visit 3, Visit 2 and Visit 4 and, Visit 3 and Visit 4.

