6.2. Baseline

Unless otherwise specified, baseline is defined as the last non-missing measurement taken same day or prior to reference start date (including unscheduled assessments) before first dose of study medication (i.e., combination therapy). Adverse Events (AEs) and medications commencing on

Document: \\weedc-vnasc01\Biosdata\Menarini\NebAm\ZZA67778\Biostatistics\Documentation\SAP\SAP_Menarini_MEIN21AmNe-Hyp001_Final_V1.0

Author: [name]

Version Number:

Final V1.0

Version Date:

11Nov2022

Template No.: CS_TP_BS016 Revision 7

Reference: CS_WI_BS005

Effective Date: 01Nov2021

the reference start date/time will be considered post-baseline, unless the start time of the AE is known to be prior to the first dosing of the study drug. Since there is no Lab assessment in Visit 2, Lab values collected at Visit 1 will be considered baseline for Lab data.

For combination therapy related analysis, the baseline will be the measurements that are taken at Visit 2 (Week 0). For safety analysis, if the measurement at visit 2 is missing or not collected, then visit 1 data will be considered.

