6.6. Common Calculations

For quantitative measurements, change from baseline will be calculated as:

- Test Value at Visit X – Baseline Value

And for change between Visit 3 and Visit 4 will be calculated as:

- Test Value at Visit 4 – Visit 3 Value

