  ODS Output TestsForLocation=test LocationCounts=LOCC_one;  
run;
```

- Exact McNemars Test

```
ods trace on;  
ods output McNemarsTest=McNemarsTest;  
proc freq data=indata order=data;  
  tables VISITX*VISITY/agree alpha=0.05 ;  
  exact mcnem;  
  weight ZZZ/zeros;  
run;
```

Document: \\neadc-vnasc01\Biosdata\Menarini\NebAm\ZZA67778\Biostatistics\Documentation\SAP\SAP_Menarini_MEIN21AmNe-Hyp001_Final_V1.0

Author: [name]

Version Number:

Final V1.0

Version Date:

11Nov2022

Template No.: CS_TP_BS016 Revision 7

Reference: CS_WI_BS005

Effective Date: 01Nov2021

- Independent sample t-test

```
ods trace on;  
proc ttest data=indata h0=0;  
class xxx;  
var change from baseline;  
run;  
ods trace off;
```

- Wicoxon Rank Sum Test

```
ods trace on;  
proc npar1way data=indata wilcoxon;  
by by_variables;  
class xxx;  
var change from baseline;  
ods output WilcoxonTest=wt;  
run;
```

- Repeated measures GLM

```
proc mixed data=indata;  
class visit sex;  
model change from baseline = Visit Age Gender BMI baseline_DBP Age*Gender  
Age*BMI_Age*baseline_DBP Gender*BMI Gender*baseline_DBP BMI*baseline_DBP  
Age*Gender*BMI_Age*Gender*baseline_DBP Age*BMI*baseline_DBP Gender*BMI*baseline_DBP  
Age*Gender*BMI*baseline_DBP;  
repeated visit;  
run;
```

Document: \\eedc-vnasc01\Biosdata\Menarini\NebAm\ZZA67778\Biostatistics\Documentation\SAP\SAP_Menarini_MEIN21AmNe-Hyp001_Final_V1.0

Author: [name]

Version Number:

Final V1.0

Version Date:

11Nov2022

Template No.: CS_TP_BS016 Revision 7

Reference: CS_WI_BS005

Effective Date: 01Nov2021

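### The 5/10 versus 5/5 mg test subtracts the same Visit 3 reading that assigned the dose, so under ordinary conditions regression to the mean favours 5/10 mg even with no dose effect

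*SAP*

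**What the plan says.** Protocol 2.1 and 12.1 say that nothing is randomised. Protocol 2.2, note e, gives the uptitration rule: "Only patients with uncontrolled BP at Visit 3 will receive NEB/AML 5/10 mg for next 4 weeks". Note d keeps controlled patients on 5/5 mg. Protocol 5 agrees that at Visit 3 controlled patients continue, "while patients with uncontrolled BP levels will be uptitrated from extemporaneous combination NEB/AML 5/5 mg" to 5/10 mg, and SAP 3.1 repeats this.

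Efficacy of 5/10 mg versus 5/5 mg between Visits 3 and 4 is a secondary objective (Protocol 4, SAP 2.2). SAP 6.6 defines the score: "And for change between Visit 3 and Visit 4 will be calculated as" the Visit 4 value minus the Visit 3 value. SAP 16.2.2.2 takes these changes in patients kept on 5/5 mg "versus patients uptitrated to the extemporaneous combination of NEB/AML 5/10 mg will be compared using independent samples t-test". Protocol 12.5.4 plans the same test and adds: "If the data is found to be non-Normal, the independent samples t-test will be replaced by Wilcoxon rank-sum test". SAP 6.5 makes tests two-sided at 5%.

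No covariate enters this comparison. The repeated-measures model in SAP 16.1.4 and 16.2.2.1 covers only changes from Visit 2. Neither document mentions regression to the mean.

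**The concern.** A patient's Visit 3 value is partly usual level and partly that day's fluctuation. Sorting on it puts upward fluctuations into the 5/10 mg group and downward ones into the 5/5 mg group. At Visit 4 the fluctuation is drawn afresh, so the first group tends to fall and the second to rise. The change score counts both movements, and the test attributes the gap to dose. Averaging three readings at a visit (Protocol 8.1) reduces error within the visit but leaves variation between visits.

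At stake is a p-value attached to a stated efficacy objective. A reader would take it as evidence that the higher amlodipine dose adds effect, and it could appear with no such effect.

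**Working it through.** **The plan's own figures.** The documents give no sample size, power or expected difference for this contrast. The figure of 216 completed patients (Protocol 12.2) belongs to the primary endpoint. It reproduces as a one-sided 5% one-sample calculation: (10 x (1.645 + 1.282) / (4 - 2))^2 = 214.1, so 215 by the normal approximation and 216 by the t distribution. Here it serves only as the trial size.

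**Expected bias.** With equal mean and SD at both visits, between-visit correlation r and no dose effect, the expected difference in change (5/10 minus 5/5) is

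-(1 - r) x (Visit 3 mean of uncontrolled minus Visit 3 mean of controlled).

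If the SDs differ, r is replaced by r x SD4/SD3.

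**Worked case (assumptions, not from the documents).** Visit 3 mean 130/80, SD 12/8, SBP-DBP correlation 0.6, r = 0.7, uncontrolled meaning either limit is reached, no entry rule.

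- Share controlled: 0.25 + arcsin(0.6)/(2 x 3.1416) = 0.352.
- Partial mean: 0.3989 x 0.5 x (1 + 0.6) = 0.319 SD units.
- Controlled DBP lies 0.319/0.352 x 8 = 7.2 mmHg below the mean. Uncontrolled lies 0.319/0.648 x 8 = 3.9 above. The gap is 11.2 (before rounding).
- Expected change: -0.3 x 3.9 = -1.2 on 5/10 mg and +0.3 x 7.2 = +2.2 on 5/5 mg. The difference is -3.4 mmHg.
- SD of change: 8 x sqrt(2 x 0.3) = 6.2. With about 140 and 76 patients, the standard error is 6.2 x sqrt(1/140 + 1/76) = 0.88. The expected t is about 3.8, so about 97% of trials are significant.

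Simulating this case gave -1.2, +2.2, -3.4 mmHg and 98%.

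**With the Visit 2 entry rule.** Only n and the cut-offs come from the documents. Assumed: mean BP on combination 131/82, 128/79 or 135/85; between-patient SD 10/7; between-patient SBP-DBP correlation 0.5; within-visit error correlation w of 0 to 0.6; r of 0.5 to 0.9. The SD of DBP change is then 7 x sqrt(2(1 - r)/r) = 9.9, 6.5 and 3.3 for r = 0.5, 0.7 and 0.9. Grade 3 patients are removed at Visits 2 and 3 (Protocol 2.1). Uncontrolled was read both as either limit and as both limits reached, since Protocol 2.1 joins the limits with an and. Visit 2 was set equal to the later mean, or 8/5 mmHg higher. There were 2,000 trials of 216 per cell. At 131/82, the spurious DBP difference and two-sided t-test rejection were:

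| r, w | Either, 8/5 shift | Either, no shift | Both, 8/5 shift | Both, no shift |
|---|---|---|---|---|
| 0.5, 0.6 | -7.8, 100% | -8.1, 100% | -7.1, 100% | -7.2, 100% |
| 0.7, 0.3 | -3.7, 94% | -4.2, 94% | -3.1, 95% | -3.5, 96% |
| 0.9, 0 | -0.9, 40% | -1.5, 44% | -0.8, 39% | -1.1, 46% |

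Over all cells the DBP difference runs from -0.7 to -8.6 mmHg and rejection from 29% to 100%; the SBP difference runs from -1.1 to -11.8 mmHg. Without the entry rule the DBP figures are -0.5 to -7.7 mmHg and 24% to 100%. At r = 0.7, w = 0.3 with the entry rule, across the assumed means, the t-test rejects in 83% to 99% and the rank-sum test in 82% to 98%, so the fallback does not help.

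**When the direction fails.** At r = 0.9, a Visit 4 SD 12% larger gives 0.9 x 1.12 = 1.01, and the simulated bias vanished (+0.03 mmHg, 5% rejection). At r = 0.7 the same increase gives 0.78, and the bias stayed (-2.8 mmHg, 71%).

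**The case against.** The strongest reply is about weight. This is an unpowered secondary comparison without multiplicity control, Protocol 12.5.4 opens by calling the secondary summaries descriptive, and every input that drives the size is assumed. A rejection range of 29% to 100% tells the sponsor little about this trial. All of that stands, and it limits severity. It does not rescue the test, because both documents go on to require it.

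A second reply is that adjustment for Visit 3 DBP and SBP would do. In linear simulations without the entry rule it gave bias of -0.09 to +0.11 mmHg and 4% to 7% false significance. With the entry rule it left about +0.1 to -0.7 mmHg and 4% to 11%. That is far better than the planned test, but the groups do not overlap in Visit 3 control status, so the estimate rests on extrapolation. It is defensible only as a labelled exploratory result.

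Two stronger readings are tempting. One is that any between-visit correlation below 1 guarantees bias towards 5/10 mg. It does not: r x SD4/SD3 must also stay below 1, without differing time trends. The other is that the Appendix 1 code, "var change from baseline", commits the plan to a Visit 4 minus Visit 2 test with bias in the opposite direction, because SAP 6.2 sets baseline at Visit 2. The code is a placeholder template. The same label appears in blocks that also serve changes from Visit 1 (SAP 16.3.2), while SAP 6.6 and 16.2.2.2 define this endpoint from Visit 3. The label needs correcting, no more.

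**Conclusion.** The concern holds for the Visit 3 to Visit 4 comparison of dose groups and should be fixed before database lock. Confidence is high that the planned test will tend to favour 5/10 mg with no dose effect, given r x SD4/SD3 below 1 and no differing time trends. Confidence in the size is low. The top of the range treats an SD of change near 10 mmHg as pure visit-to-visit noise, so it is an upper scenario. The benchmark is 2.5% false significance in favour of 5/10 mg, since tests are two-sided.

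A reader might infer that the primary result is compromised in the same way. It does not use this contrast, so the point does not reach it. Nor does the point show that 5/10 mg lacks added effect, only that this test cannot separate such an effect from the artefact.

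A separate side point: Protocol 7 ties 5/10 mg to uncontrolled patients "whose adherence to the therapies ranges from 80% to 120%) at Visit 2", whereas Protocol 2.2, Protocol 5 and SAP 3.1 use Visit 3. These passages must be reconciled.

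**What to change.** In SAP 16.2.2.2, delete the sentences on the between-group t-test, normality check and rank-sum test. Replace them with:

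> The Visit 3 to Visit 4 change in sitting DBP and SBP will be reported separately for patients kept on 5/5 mg and patients uptitrated to 5/10 mg, as mean with 95% CI and the planned descriptive statistics, with no between-group p-value. Because dose was assigned by Visit 3 BP, each change includes regression to the mean and their difference does not estimate a dose effect.

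In SAP 3.3, record the departure from Protocol 12.5.4 and from the synopsis (Statistical Assumptions), and state that the 5/10 versus 5/5 mg objective and endpoint (Protocol 4, SAP 2.2 and 16.2.1) will be addressed descriptively only. Remove the independent t-test and rank-sum templates from Appendix 1; if either is kept, relabel its variable as Visit 4 minus Visit 3. Any estimate adjusted for Visit 3 DBP and SBP should be labelled exploratory, with the extrapolation stated.

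The cost is one SAP paragraph, one SAP 3.3 entry and two code blocks. Dosing and data collection do not change. The sponsor loses one between-group p-value. Protocol 12.7 ties a substantial amendment to changes in the primary endpoint or primary analyses, and SAP 3.3 already records a changed secondary test. Because Protocol 12.6 requires an amendment for changes to the Protocol, the sponsor should confirm that a SAP 3.3 entry is enough. Any correction to the text of Protocol 7 falls under 12.6.

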16.2.2.3. Number and proportion of patients achieving the BP goal

The number of patients achieving the BP goal (sitting BP < 130/80 mmHg) will be summarized for Visit 2 (Week 0), Visit 3 (Week 4) and Visit 4 (Week 8) along with percentage and 95% CI (Clopper Pearson). A p-value using exact McNemar's test will be presented to compare the proportion of patients achieving the BP goal (sitting BP < 130/80 mmHg) between Visit 2 and Visit 3 as well as Visit 2 and Visit 4. A p-value using McNemar's test will be presented to compare the proportion of patients achieving the BP goal (sitting BP < 130/80 mmHg) between Visit 3 and Visit 4.

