### Withdrawal of patient from the study

The patient may withdraw from the study at any time without explanation, without losing the right to future medical care. The participation of the patient may, at any moment, be terminated by the Investigator, if considered appropriate.

A patient can be withdrawn during the study for any of the following reasons:

- Any AE, which required treatment and study termination for the patient according to the Investigator's judgment.
- Abnormal renal function or liver enzyme parameters as described in Section 8.2.3.
- Patient becomes pregnant during the study.
- Request of the patient (without giving any reason).
- Investigator deems it to be in the best interest of the patient to discontinue.
- Failure to adequately comply with the dosing, evaluations, or other requirements of the study.
- If the patient meets an exclusion criterion (newly developed or not previously recognized) that precludes further study participation.
- Use of any prohibited medication that in the opinion of the Investigator or Sponsor necessitates the patient being withdrawn.

The reason for the withdrawal of study treatment, or withdrawal from the study must be well documented in the source documents and in the eCRF page and should capture the date and the specific underlying reason for discontinuation of study treatment or patient discontinuation/withdrawal.

MENARINI	Corporate Medical Department		
	Р	Protocol Template	
Identification Number	Version Number	State	Effective date
FORM-000050125	2.0, CURRENT	Effective	08 Jan, 2021

*Study Code:* MEIN/21/AmNe-Hyp/001

Patients who discontinue from the study early will be asked, anyway, to complete all the assessments of Visit 4. Patients may discontinue the study treatment, but remain in the study for follow-up, especially for safety study endpoints (if applicable).

If a patient has been discontinued/withdrawn due to an AE, the Investigator must immediately notify the relevant pharmacovigilance contact (see Section 9.9) and should be followed-up until the AE is resolved or the Investigator deems further observations or examinations as no longer medically indicated.

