5.2. Modified Intent-to-Treat (mITT) Population

The Modified Intent-to-Treat (mITT) population will contain all patients who are in the Enrolled population, receive at least one dose of combination therapy, and have at least baseline and Week 8 assessments with primary efficacy data.

Document: \\eedc-vnasc01\Biosdata\Menarini\NebAml\ZZA67778\Biostatistics\Documentation\SAP\SAP_Menarini_MEIN21AmNe-Hyp001_Final_V1.0

Author: [name]

Version Number:

Final V1.0

Version Date:

11Nov2022

Template No.: CS_TP_BS016 Revision 7

Reference: CS_WI_BS005

Effective Date: 01Nov2021

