5.4. Per-Protocol (PP) Population

The Per-Protocol (PP) population will contain all patients included in the Safety population who do not have any major protocol deviations that could affect the primary efficacy analyses and have at least baseline (Week 0) and Week 8 assessments with primary efficacy data.

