6.3. Retests, Unscheduled Visits and Early Termination Data

In general, for by-visit summaries, data recorded at the nominal visit will be presented. Unscheduled measurements will not be included in by-visit summaries. Listings will include scheduled, unscheduled, retest and early discontinuation data.

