7. STATISTICAL CONSIDERATIONS

Summaries will include descriptive statistics for continuous variables (sample size [n], mean, standard deviation [SD], median, minimum and maximum) and for categorical variables (frequency [n] and percentage), unless otherwise stated in the relevant section. Percentages will be based on the number of patients within the relevant analysis population and treatment arm, or the number of patients with data available where relevant.

If the original data has N decimal places, then the summary statistics will have the following decimal places:

Minimum and maximum: N

Mean, median, Q1, Q3, confidence intervals, ratios: N + 1

SD: N + 2

Percentages will be reported to one decimal place. P-values should be reported to three decimal places, except values <1.000 but >0.999 will be presented as '>0.999' (e.g., 0.9998 is presented as >0.999); and values <0.001 will be presented as '<0.001' (e.g., 0.0009 is presented as <0.001)

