7.3. Missing Data

All analyses will be performed on observed data. Missing data will not be imputed for this study.

Document: \\eedc-vnasc01\Biosdata\Menarini\NebAml\ZZA67778\Biostatistics\Documentation\SAP\SAP_Menarini_MEIN21AmNe-Hyp001_Final_V1.0

Author: [name]

Version Number:

Final V1.0

Version Date:

11Nov2022

Template No.: CS_TP_BS016 Revision 7

Reference: CS_WI_BS005

Effective Date: 01Nov2021

Copyright © 2009, 2010, 2012, 2016, 2018, 2019, 2021 IQVIA. All rights reserved. The contents of this document are confidential and proprietary to IQVIA Holdings Inc. and its subsidiaries. Unauthorized use, disclosure or reproduction is strictly prohibited.

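### The secondary BP-goal rates use only patients with a Week 8 reading, so other treated patients leave the Visit 4 rate and also lose an observed Visit 3 result

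*SAP*

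**What the plan says.** SAP 16.2.2.3 sets out counts, percentages, Clopper-Pearson intervals and McNemar comparisons for the BP goal: "The number of patients achieving the BP goal (sitting BP < 130/80 mmHg) will be summarized for Visit 2 (Week 0", continuing to Visits 3 and 4. The analysis sets come from SAP 16.2: "Secondary efficacy variables will be analyzed using both the mITT as well as the PP population".

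Both sets look ahead to Week 8:

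- mITT patients must "receive at least one dose of combination therapy, and have at least baseline and Week 8 assessments with primary efficacy data" (SAP 5.2).
- PP patients must "have at least baseline (Week 0) and Week 8 assessments with primary efficacy data" (SAP 5.4). Protocol 12.3 has no such condition for PP. The SAP added it and lists the change in SAP 3.3.

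Four further provisions bear on the point:

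- **Missing data:** "All analyses will be performed on observed data. Missing data will not be imputed for this study" (SAP 7.3; Protocol 12.5.8 agrees). Section 16.2.2.3 has no rule for counting a missing reading as not at goal.
- **Denominators:** "Percentages will be based on the number of patients within the relevant analysis population and treatment arm", or on patients with data where relevant (SAP 7).
- **By-visit summaries:** "data recorded at the nominal visit will be presented" (SAP 6.3). Appendix 1 lists Early Termination as a visit separate from Visit 4.
- **Early discontinuers:** "Patients who discontinue from the study early will be asked, anyway, to complete all the assessments of Visit 4" (Protocol 10).

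**The concern.** A Week 4 result should not depend on whether the patient has a reading four weeks later. Here it does. Patients with a Visit 3 reading and no Week 8 reading are dropped from the Visit 3 rate, although nothing about their Visit 3 result is missing.

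The losses are not plainly unrelated to outcome. The note to the Study Scheme (Protocol 2.1) says that patients with Grade 3 BP are withdrawn at Visits 2 and 3. Anyone withdrawn at Visit 3 on that ground has an observed reading that is, by definition, not at goal.

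PP offers no check on this, because under the SAP it carries the same Week 8 condition as mITT. Agreement between the two sets says nothing about patients lost before Week 8.

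Protocol 4 justifies this endpoint as a key marker of whether treatment works. A reader will take an mITT control rate to describe patients given the combination, whereas it describes those with a Week 8 reading.

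**Working it through.** **What the plan's figures give.** The documents state no expected goal rate and no loss rate after Visit 2. The only attrition figure is 25%, covering screen failure and drop-out from Visit 1 to Visit 4 (Protocol 12.2). It reproduces the screening number: 216 / 0.75 = 288, close to the stated 290. It cannot be read as loss after Visit 2, because it also absorbs screening and run-in losses. Entry to the assessment period is capped at 110 per monotherapy, or 220 in all, and about 216 completers are planned. If 220 enter and 216 complete, the loss is 4/220 = 1.8%. Protocol 12.2 also describes 216 as the number entering the assessment period, so a larger loss is possible.

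**Who is removed.** Take a patient with a combination dose, a Visit 2 reading, a Visit 3 reading and no Week 8 reading.

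1. SAP 5.2 and 5.4 exclude the patient from mITT and PP, hence from every result in 16.2.2.3.
2. In the Visit 2 to Visit 3 McNemar test, a complete observed pair is discarded.
3. In the two tests involving Visit 4, the pair would be incomplete on observed data in any case.

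**Visit 4.** Let d be the share of combination starters without Week 8 data, and p4 the goal rate among those with it. If patients without data count as not at goal, the rate over all starters is p4 × (1 − d). All values of p4 are assumptions, as is every d other than 1.8%.

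| p4 | d = 1.8% | 5% | 10% | 15% | 25% (extreme) |
|---|---|---|---|---|---|
| 30% | 29.5% | 28.5% | 27.0% | 25.5% | 22.5% |
| 50% | 49.1% | 47.5% | 45.0% | 42.5% | 37.5% |
| 60% | 58.9% | 57.0% | 54.0% | 51.0% | 45.0% |

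The last column puts the whole 25% allowance after Visit 2.

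**Visit 3.** Let p3 be the Visit 3 goal rate in patients with a Week 8 reading and q the rate in those with a Visit 3 but no Week 8 reading. Let e be the second group's share of all observed Visit 3 readings. The rate over all observed readings is (1 − e) × p3 + e × q. Assume p3 = 40% and e = 10%:

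- q = 0%: 0.9 × 40 + 0.1 × 0 = 36.0%
- q = 40%: 40.0%
- q = 60%: 42.0%
- q = 100%: 46.0%

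With e = 1.8% the range is 39.3% to 41.1%. The reported 40% is too high only if the removed patients did worse than those kept.

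**The case against.** **These patients are not lost from the whole SAP.** A reader might infer that they are counted nowhere. The documents do not support that. SAP 16.3.2 produces exploratory goal rates at Visits 2, 3 and 4 on the Enrolled population, which needs no Week 8 reading. SAP 18.5 summarises sitting BP by visit on the Safety population, and SAP 9.1 tabulates reasons for exclusion. This stands, but it only partly mitigates. The Enrolled tables are split by prior-therapy group or subgroup, and they include patients who never started the combination. SAP 7 also leaves their denominator open. No specified table gives the overall rate among combination starters.

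**Stopping treatment is not the trigger.** A reader might infer that anyone who stops the combination drops out of the rate. The criterion is a missing Week 8 assessment. A patient may stop treatment and stay in the study, and early discontinuers are asked for the Visit 4 assessments. Whether those count as Week 8 is unstated, and SAP 6.3 with Appendix 1 points against it. This stands, and the missing mapping belongs to the point.

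**Overstatement is not proved.** At Visit 3 the shift can go either way, because patients who leave for other reasons may have been at goal. At Visit 4 overstatement follows only if missing is defined as not at goal. That is a choice of estimand, not a fact about an unmeasured patient, and it conflicts with the no-imputation rule. This stands.

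**The effect may be small.** On the 220 and 216 figures it is about one point. Conclusions against Visit 2 are also unlikely to change, since SAP 3.3 notes that the Visit 2 goal rate is zero by the entry rule. This stands as a limit on importance. It does not justify discarding observed Visit 3 data.

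**Conclusion.** The point holds for the secondary endpoint in SAP 16.2.2.3. Both analysis sets condition on a Week 8 assessment, so the Visit 3 rate is selected on a later event and the Visit 4 rate describes only patients with Week 8 data. Upward bias at Visit 3 is likely, because some of those removed may be Grade 3 patients known not to be at goal, but it is not assured.

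The size is not derivable from the documents. Counting missing as not at goal at Visit 4, an assumed 60% becomes 58.9% if 220 enter and 216 complete, and 54.0% under an assumed 10% loss. At Visit 3, with an assumed 40% rate and 10% removed, the rate on all observed readings lies between 36.0% and 46.0%. The defect is worth correcting on principle and because correction is cheap. The documents do not show that the reported rates will be badly wrong.

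**What to change.** In SAP 16.2.2.3:

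1. Define the set as all patients with at least one combination dose and a Visit 2 BP.
2. Use every observed Visit 3 reading for the Visit 3 rate and for the Visit 2 to Visit 3 McNemar test. State the denominator.
3. Report the Visit 4 rate over the whole set with a missing reading counted as not at goal, and show the observed-case rate beside it. State which version feeds the tests involving Visit 4.
4. State whether Visit 4 assessments done at early termination count as Week 8.
5. Record the change in SAP 3.3, with an explicit exception to the no-imputation rule in SAP 7.3 and Protocol 12.5.8. Only step 3 needs that exception.

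No new data are needed. Protocol 12.7 calls for a substantial amendment when the primary endpoint or primary analyses change, and this change touches neither. The cost is SAP wording, one more table and a somewhat lower quoted Visit 4 rate.
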